10.6 Measures to Minimize Bias

10.6.1 Enrollment/Randomization/Masking Procedures

In order to produce treatment groups in which the distributions of prognostic factors, known and unknown, are similar and minimize bias, we will randomize participants to treatment groups. We will generate a randomization schedule using SAS 9.3 (SAS Institute, Cary NC). Additionally, participants, investigator, treatment team and analyst will be blinded to treatment group. The generated randomization schedule will be provided to the research pharmacy who will assign which arm is the treatment groups and reveal assignment after analysis is complete. The pharmacy will carry out the blinding as the drugs (ointments) will be aliquoted into unmarked containers labeled with the arm (A or B). The research pharmacy will provided drug to the investigators when a subject is enrolled in blinded form. The A/B group identifier (retapamulin vs placebo) will not be revealed until the study is completed and data analyzed. There are no anticipated obvious drug effects from the retapamulin or placebo that would imperfect blinding.

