10.4.4 Safety Analyses

Patients will be monitored for the occurrence of possible adverse events using a standardized data collection form prior to hospital discharge. All serious events which many potentially be adverse reactions (anaphylaxis, serious rash or death) will be assessed by the primary investigator. The study team and the NYU SOM Institutional Review Board will be notified within one day of identification of the event by study personnel.

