10.6.2 Evaluation of Success of Blinding

If treatment group assignment is unknown to all subjects, investigators, treatment team and analyst for the duration of the study, blinding will be considered a success.

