10.6.3 Breaking the Study Blind/Participant Code

Criteria to break the study blind for an individual include serious adverse events such as anaphylaxis in the particular patient. Study blind would be broken for all participants if recurrent serious adverse events are observed among numerous participants. Serious adverse effects are not expected with the use of this study drug. Intentional and unintentional breaking of the blind will be reported by the PI/co-investigator to all members of the study team, the IRB, and the industry sponsor.

11 Source Documents and Access to Source Data/Documents

Source data is all information, original records of clinical findings, observations, or other activities in a clinical trial necessary for the reconstruction and evaluation of the trial. Source data are contained in source documents. Examples of these original documents, and data records include: hospital records, clinical and office charts, laboratory notes, memoranda, subjects' diaries or evaluation checklists, pharmacy dispensing records, recorded data from automated instruments, copies or transcriptions certified after verification as being accurate and complete, microfiches, photographic negatives, microfilm or magnetic media, x-rays, subject files, and records kept at the pharmacy, at the laboratories, and at medico-technical departments involved in the clinical trial. It is acceptable to use CRFs as source documents. If this is the case, it should be stated in this section what data will be collected on CRFs and what data will be collected from other sources.

The study case report form (CRF) is the primary data collection instrument for the study. All data requested on the CRF must be recorded. All missing data must be explained. If a space on the CRF is left blank because the procedure was not done or the question was not asked, write "N/D". If the item is not applicable to the individual case, write "N/A". All entries should be printed legibly in black ink. If any entry error has been made, to correct such an error, draw a single straight line through the incorrect entry and enter the correct data above it. All such changes must be initialed and dated. DO NOT ERASE OR WHITE OUT ERRORS. For clarification of illegible or uncertain entries, print the clarification above the item, then initial and date it.

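### Containers carry one of two shared arm letters, so one disclosed code break could decode every assignment and the single-participant break in 10.6.3 is not contained

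*Combined protocol and SAP*

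**What the plan says.** **Labels.** In 10.6.1 the research pharmacy decides which letter is which treatment, and the ointments are "aliquoted into unmarked containers labeled with the arm (A or B". The same section adds: "The A/B group identifier (retapamulin vs placebo) will not be revealed until the study is completed and data analyzed". Section 10.3 lists the blinded A/B arm as a variable for each participant. No participant-specific kit number is described. Sections 6.1.2 and 6.1.4 call the containers unlabeled, and 6.2 calls them unidentifiable.

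**Code breaks.** Section 10.6.3 has two levels. For one child: "Criteria to break the study blind for an individual include serious adverse events such as anaphylaxis in the particular patient". For the whole trial: "Study blind would be broken for all participants if recurrent serious adverse events are observed among numerous participants". It then states: "Intentional and unintentional breaking of the blind will be reported by the PI/co-investigator to all members of the study team", and also to the IRB and the industry sponsor. It does not say who receives the treatment identity.

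**Blinding standard.** Section 10.6.2 counts blinding as successful if "treatment group assignment is unknown to all subjects, investigators, treatment team and analyst for the duration of the study".

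**People.** Section 6.2 has the PI or co-investigator distribute the containers at Visit 1. Section 14.1 has them move the paper data, including the tracking of study agents, into the electronic database as the study proceeds. Section 10.4.4 says: "All serious events which many potentially be adverse reactions (anaphylaxis, serious rash or death) will be assessed by the primary investigator".

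**The concern.** The plan assumes that one child can be unblinded while everyone else stays masked. A shared letter does not allow that. Once a person knows what one lettered container held, every other container with that letter is known, and so is every container with the other letter.

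The people most likely to hold the letters also assess the children. If the code were decoded part-way through, knowledge of treatment could influence the examination of nares and peri-rectal area, the swab collection, and the grading of adverse events for severity and relatedness (8.3), for children still to be assessed.

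Culture reading is not clearly protected either. Swabs and plates carry a study code number (7.2.3), but the study investigators process them (7.1.1, 7.2.3), and the PI and co-investigator keep the file that links code to patient (13.4). The culture result is the primary endpoint.

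**Working it through.** **1. Number of assignments.** Section 10.5 gives 22 per group and adds 20%: 22 × 1.2 = 26.4, rounded up to 27 per arm, and 2 × 27 = 54. This reproduces the plan's figure. It is taken as given and is not in dispute here.

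**2. What one letter–treatment pair reveals.** There are only two ways to match {A, B} to {retapamulin, placebo}, so one known pair settles which applies. Suppose the break comes after k children have been randomised, and the person who learns the treatment holds the letters:

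- decoded at once: k
- decoded later, as containers are dispensed: 54 − k
- total: k + (54 − k) = 54, that is, 1 + 53 others

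With a unique number per child and no visible arm letter, the same break directly decodes 1 + 0 others.

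**3. How many children still have assessments to come.** This is fewer than 54, because some will have finished. Assume even accrual over the 2-year study duration and about 6 weeks (42 days) per child, both from the protocol summary. The number in follow-up at any time is then 54 × 42/730 = 3.1, or about 3. Children still open to influence ≈ 3 + (54 − k):

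| Break after k randomised | Not yet randomised (54 − k) | Still to be assessed |
|---|---|---|
| 14 | 40 | about 43 |
| 27 | 27 | about 30 |
| 40 | 14 | about 17 |

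**4. Who could hold both pieces of information.**

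- *Letters:* the PI and co-investigator, through the containers (6.2) and the data transfer (14.1). Section 14.1 does not name the A/B field, but it covers agent tracking and assigns the transfer to them.
- *Treatment of the child whose code is broken:* not stated. The PI assesses the triggering event (10.4.4) and the PI or co-investigator reports the break (10.6.3), so they are close to it. No text says that they are told the treatment, and none says that they are not.

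**5. Comparison with the plan's own standards.** Any disclosed individual break already fails the 10.6.2 criterion for that child. With shared letters it fails for every child, and the commitment in 10.6.1 to keep the A/B meaning hidden until the data are analysed is lost at the same time.

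**The case against.** The strongest reply is that harm needs three things together: a code break, disclosure of the treatment to someone meant to be blinded, and that person holding the letters. The documents provide for only the first. Section 10.6.3 requires the break to be reported, not the treatment. Assessing a serious event does not require the PI to be unblinded. The identity might go only to someone who holds no letters. Section 10.6.3 also does not expect serious adverse effects. All of this stands, and it makes the point conditional.

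A second reply is that the documents disagree on whether a dispensed container shows a letter at all, since 6.1.2, 6.1.4 and 6.2 call it unlabeled or unidentifiable. This stands as an inconsistency to resolve. It does not remove the problem, because 10.6.1 states the letter explicitly and 10.3 stores it for each child.

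Three stronger readings are tempting, and the documents do not support them:

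- *A single break will unblind the study team.* Nothing says that the treatment is disclosed to them.
- *Someone in the team holds all the letters from the start.* This would rest only on the pronoun in "We will generate a randomization schedule using SAS 9.3". No text says that a copy is kept, and the pharmacy decides which letter is which treatment, so the schedule alone reveals no treatment.
- *A break is likely.* The documents give no break rate, so no probability can be attached.

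**Conclusion.** The concern holds as a conditional weakness in the masking scheme. If a person who holds the letters learns one child's treatment, all 54 assignments can be decoded, 53 of them for children whose blind was not meant to be broken. The separation in 10.6.3 between an individual and a trial-wide break then no longer exists. The assessments that could be influenced are those of roughly 43, 30 or 17 children for a break after 14, 27 or 40 randomisations, under the even-accrual assumption.

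A reader might infer that the planned blind is already broken, or that the primary result would be biased for all 54 children. Neither follows. The event is expected to be rare, disclosure is not prescribed, and children who have finished follow-up cannot be affected at examination or swabbing. Nor do the coded plates show that culture reading is safe, given who processes them and who holds the link file.

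This is a cheap improvement that should be made, not a defect that invalidates the design.

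**What to change.** - **Labels (10.6.1):** the research pharmacy labels each container with a unique participant or kit number and no arm letter. It holds the allocation list, with code-break records that each open one participant only.
- **Consistency:** reconcile the descriptions of the containers in 6.1.2, 6.1.4 and 6.2 with 10.6.1.
- **Data (10.3):** keep the A/B field out of the investigators' working database. Give it to the blinded analyst as a group code only after data lock. The pharmacy still reveals its meaning after analysis, as already planned.
- **Break reports (10.6.3):** state that the report to the study team gives the fact of the break and not the treatment, and name who does receive the treatment identity.

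The cost is 54 individual labels in place of two label types, 54 one-participant code-break records, and wording edits in 6.1.2, 6.1.4, 6.2, 10.3, 10.6.1 and 10.6.3. Sample size, visits and analysis are unchanged.

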10.6.2 Evaluation of Success of Blinding

If treatment group assignment is unknown to all subjects, investigators, treatment team and analyst for the duration of the study, blinding will be considered a success.

10.6.3 Breaking the Study Blind/Participant Code

Criteria to break the study blind for an individual include serious adverse events such as anaphylaxis in the particular patient. Study blind would be broken for all participants if recurrent serious adverse events are observed among numerous participants. Serious adverse effects are not expected with the use of this study drug. Intentional and unintentional breaking of the blind will be reported by the PI/co-investigator to all members of the study team, the IRB, and the industry sponsor.

11 Source Documents and Access to Source Data/Documents

Source data is all information, original records of clinical findings, observations, or other activities in a clinical trial necessary for the reconstruction and evaluation of the trial. Source data are contained in source documents. Examples of these original documents, and data records include: hospital records, clinical and office charts, laboratory notes, memoranda, subjects' diaries or evaluation checklists, pharmacy dispensing records, recorded data from automated instruments, copies or transcriptions certified after verification as being accurate and complete, microfiches, photographic negatives, microfilm or magnetic media, x-rays, subject files, and records kept at the pharmacy, at the laboratories, and at medico-technical departments involved in the clinical trial. It is acceptable to use CRFs as source documents. If this is the case, it should be stated in this section what data will be collected on CRFs and what data will be collected from other sources.

The study case report form (CRF) is the primary data collection instrument for the study. All data requested on the CRF must be recorded. All missing data must be explained. If a space on the CRF is left blank because the procedure was not done or the question was not asked, write "N/D". If the item is not applicable to the individual case, write "N/A". All entries should be printed legibly in black ink. If any entry error has been made, to correct such an error, draw a single straight line through the incorrect entry and enter the correct data above it. All such changes must be initialed and dated. DO NOT ERASE OR WHITE OUT ERRORS. For clarification of illegible or uncertain entries, print the clarification above the item, then initial and date it.

Access to study records will be limited to IRB-approved members of the study team. The investigator will permit study-related monitoring, audits, and inspections by the IRB/EC, the sponsor, government

CONFIDENTIAL

This material is the property of the NYU School of Medicine and Langone Medical Center. Do not disclose or use except as authorized in writing by the study sponsor

regulatory bodies, and University compliance and quality assurance groups of all study related documents (e.g. source documents, regulatory documents, data collection instruments, study data etc.). The investigator will ensure the capability for inspections of applicable study-related facilities (e.g. pharmacy, diagnostic laboratory, etc.).

Participation as an investigator in this study implies acceptance of potential inspection by government regulatory authorities and applicable University compliance and quality assurance offices.

12 Quality Assurance and Quality Control

QA/QC will be monitored by [name], MPH. All planned study related procedures, data handling and analysis will be assessed at the initiation of the trial and semiannually to ensure the trial is performed and data is generated, documented and reported in compliance with GCP and the applicable regulatory requirements. QC procedures will be implemented beginning with the data entry system and data QC checks that will be run on the database will be generated. Any missing data or data anomalies will be communicated to the PI for clarification/resolution.

Following written SOPs, the monitors will verify that the clinical trial is conducted and data are generated, documented (recorded), and reported in compliance with the protocol, GCP, and the applicable regulatory requirements (e.g., Good Laboratory Practices (GLP), Good Manufacturing Practices (GMP)).

The investigational site will provide direct access to all trial related sites, source data/documents, and reports for the purpose of monitoring and auditing.

13 Ethics/Protection of Human Subjects

13.1 Ethical Standard

The investigator will ensure that this study is conducted in full conformity with Regulations for the Protection of Human Subjects of Research codified in 45 CFR Part 46, 21 CFR Part 50, 21 CFR Part 56, and/or the ICH E6.

13.2 Institutional Review Board

The protocol, informed consent form(s), recruitment materials, and all participant materials will be submitted to the IRB for review and approval. Approval of both the protocol and the consent form must be obtained before any participant is enrolled. Any amendment to the protocol will require review and approval by the IRB before the changes are implemented to the study. All changes to the consent form will be IRB approved; a determination will be made regarding whether previously consented participants need to be re-consented.

13.3 Informed Consent Process

13.3.1 Consent/Accent and Other Informational Documents Provided to Participants

Consent forms describing in detail the study agent, study procedures, and risks are given to the participant and written documentation of informed consent is required prior to starting intervention/administering study product.

The following consent materials are submitted with this protocol in the appendix:

Informed Consent
Assent (Age 7-11)

CONFIDENTIAL

This material is the property of the NYU School of Medicine and Langone Medical Center. Do not disclose or use except as authorized in writing by the study sponsor
Interventional Template Version: 28 APR 2017

Assent (Age 12-14)
Assent (Age 15-17)

13.3.2 Consent Procedures and Documentation

Informed consent and assent will be obtained from all subjects by the PI and trained study co-investigators. The consent forms (informed consent, and age specific assents) are included in the appendix. Informed consent will be obtained from the participant's parent/legal guardian and assent will be obtained if able from the participant. The study staff will explain the study rationale, procedures, risks and benefits. Subjects will be given ample time to read and review the consent/assent forms and to ask questions to ensure comprehension of the consent/assent, the scientific background of the study, and the procedures required of them.

Since the population being studied may not be able to provide informed consent in English, the informed consent and assent forms will be translated into the subject's preferred language and submitted to the IRB for review before a non-English speaking subject is enrolled. A translator will be used when a non-English speaking subject is taken through the informed consent and assent process. For non-English speaking children capable of providing assent, assent will be obtained verbally and documented accordingly in the research record. For English speaking children capable of providing assent, the age-appropriate assent will be signed.

The following individuals are authorized to obtain consent:

[name].,M.P.H. – Co-investigator
[name]. – Principal Investigator
[name], MBA
[name], MPH

Informed consent is a process that is initiated prior to the individual's agreeing to participate in the study and continues throughout the individual's study participation. Extensive discussion of risks and possible benefits of participation will be provided to the participants and their families. Consent forms will be IRB-approved and the subject's parent/guardian will be asked to read and review the document while children will be asked to review the age-appropriate assent form. The investigator will explain the research study to the participant and the parent/guardian and answer any questions that may arise. All participants and parent/guardians will receive a verbal explanation in terms suited to their comprehension of the purposes, procedures, and potential risks of the study and of their rights as research participants. Participants' parents/guardians will have the opportunity to carefully review the written consent form and ask questions prior to signing and the children will in turn have the opportunity to review the assent form and ask questions. The participants and their parent/guardian should have the opportunity to discuss the study with their families or doctors or think about it prior to agreeing to participate. The participants' parent/guardian will sign the informed consent document prior to any procedures being done specifically for the study and the children will sign the appropriate assent form. The participants' parent/guardian may withdraw consent at any time throughout the course of the trial. A copy of the signed informed consent and assent document will be given to the participants' parent/guardian for their records. The rights and welfare of the participants will be protected by emphasizing to them that the quality of their medical care will not be adversely affected if they decline to participate in this study.

A copy of the signed informed consent document and assent form will be stored in the subject's research record. The consent and assent process, including the name of the individual obtaining consent and assent, will be thoroughly documented in the subject's research record. Any alteration to the standard consent process (e.g. use of a translator, consent document presented orally, etc.) and the justification for such alteration will likewise be documented.

CONFIDENTIAL

13.4 Participant and Data Confidentiality

Data will be kept secure and minimal personal identification information will be collected which will then be de-identified in the study database. Each subject enrolled in the study will be assigned a unique code. All samples and data collected will be labeled with the subject's assigned code. No other names or identifiers will be on these samples or data. A file linking the study code to the patient will be maintained by the study PI and co-investigator to enable retrieval of additional information if needed. This file will be stored in a locked cabinet and password protected database created specifically for this study. Only the PI and essential research personnel will have access to the cabinet and database. No individual identifiable information from the data collected will be published. Only aggregate data will be presented publicly to avoid identification of any individual subject. Project staff will verify that all research materials are collected before leaving a research site.

Information about study subjects will be kept confidential and managed according to the requirements of the Health Insurance Portability and Accountability Act of 1996 (HIPAA). Those regulations require a signed subject authorization informing the subject of the following:

- What protected health information (PHI) will be collected from subjects in this study
- Who will have access to that information and why
- Who will use or disclose that information
- The rights of a research subject to revoke their authorization for use of their PHI.

In the event that a subject revokes authorization to collect or use PHI, the investigator, by regulation, retains the ability to use all information collected prior to the revocation of subject authorization. For subjects that have revoked authorization to collect or use PHI, attempts should be made to obtain permission to collect at least vital status (i.e. that the subject is alive) at the end of their scheduled study period.

Participant confidentiality is strictly held in trust by the participating investigators, their staff, and the sponsor(s) and their agents. This confidentiality is extended to cover testing of biological samples and genetic tests in addition to the clinical information relating to participants. Therefore, the study protocol, documentation, data, and all other information generated will be held in strict confidence. No information concerning the study or the data will be released to any unauthorized third party without prior written approval of the sponsor.

The study monitor, other authorized representatives of the sponsor, representatives of the IRB or pharmaceutical company supplying study product may inspect all documents and records required to be maintained by the investigator, including but not limited to, medical records (office, clinic, or hospital) and pharmacy records for the participants in this study. The clinical study site will permit access to such records.

The study participant's contact information will be securely stored at each clinical site for internal use during the study. At the end of the study, all records will continue to be kept in a secure location for as long a period as dictated by local IRB and Institutional regulations.

Study participant research data, which is for purposes of statistical analysis and scientific reporting, will be transmitted to and stored at NYU Langone Medical Center. This will not include the participant's contact or identifying information. Rather, individual participants and their research data will be identified by a unique study identification number. The study data entry and study management systems used by clinical sites and by NYU Langone Medical Center research staff will be secured and password protected. At the end of the study, all study databases will be de-identified and archived at the NYU Langone Medical Center.

